10.2 Statistical analysis

For the primary objective, we will estimate the response rate and provide the associated 95% confidence interval. For the secondary objectives, we will use the Kaplan-Meier method to estimate the distributions of time to response and progression-free survival. We will apply multivariate analysis to further examine effects of factors that are potentially related to these outcomes.

11 Registration Procedures

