1.5 Study Rationale

Given the single-agent activity demonstrated with both temozolomide and RAD001 in patients with neuroendocrine tumors, evaluation of a combination of these two agents in neuroendocrine tumors is warranted. The activity of temozolomide appears to be limited primarily to patients with pancreatic neuroendocrine tumors, based on our recent clinical experience. We therefore propose a phase I/II study to evaluate the efficacy and safety of RAD001 in combination with temozolomide in patients with metastatic pancreatic neuroendocrine tumors.

Although the combination of RAD001 and gemcitabine was associated with toxicity, RAD001 has been studied in combination with paclitaxel without evidence of synergistic toxicity. This data, as well as the markedly different mechanisms of action of RAD001 and temozolomide, suggest that combining these two agents at standard doses, with appropriate safety monitoring, may be feasible. However, to ensure that we do not miss unexpected toxicities, we will initiate treatment at a dose level below the anticipated phase II dose. Three patients will be treated with RAD001 orally at a dose of 5 mg daily, in combination with temozolomide at a standard dose (150 mg/m² daily for 7 days, followed by a 1 week break). Patients will be observed for toxicity. If no dose limiting toxicity is observed in this first cohort, subsequent patients will receive the full anticipated phase II dose of RAD001 10 mg daily, in combination with temozolomide 150 mg/m² daily for 7 days, every other week. To minimize the risk of lymphopenia-related opportunistic infections, temozolomide therapy will be limited to a maximum of 6 months, and all patients will receive PCP prophylaxis.

2 Study objectives

Primary

- To determine the objective response rate of RAD001 in combination with temozolomide in patients with advanced (unresectable or metastatic) pancreatic neuroendocrine tumors.

Secondary

- To determine the duration of response to the combination of RAD001 and temozolomide in patients with advanced pancreatic neuroendocrine tumors.
- To determine the safety and tolerability of the combination of RAD001 and temozolomide in patients with advanced pancreatic neuroendocrine tumors.
- To determine the progression free survival and overall survival of patients receiving the combination of RAD001 and temozolomide.

3 Investigational plan

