4.3 Monitoring of suspected toxicities

Patients whose treatment is interrupted or permanently discontinued due to an adverse event or abnormal laboratory value suspected to be related to RAD001 or temozolomide must be followed at least weekly until the adverse event or abnormal laboratory resolves or returns to grade 1. If a patient requires a dose delay of > 21 days from the intended day of the next scheduled dose, then the patient must be discontinued from the study.

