5.1.3.1 Table of required data

Table 5.1. Evaluation and visit schedule

Examination	Screening		Every Cycle	Cycles 1- 6	Every 2 cycles	End
	-28 days	-14 days	Day 1	Day 15		
Screening ^a		X				
History		X	X*	X		X
Physical Exam		X	X*	X		X
Vital Signs		X	X*	X		X
Height		X				
Weight		X	X*	X		X
ECOG PS		X	X*			X
Pregnancy Test ^b		X				
Hematology ^c		X	X*	X		X
Serum Chemistry ^d		X	X*			X
Serum Lipid Profile ^e		X			X	X
Radiologic Assessment of Tumor Burden ^f	X				X	X
Secretory proteins, serum chromogranin ^g	X				X	X
Prior/concomitant medication		X	continuous -----			
Adverse events		X	continuous -----			

* Screening tests do not need to be repeated for cycle 1.

^a Screening includes review of: demography/informed consent, inclusion/exclusion criteria, relevant medical history/concomitant medications, diagnosis and extent of cancer

^b For women of child-bearing potential: Women of childbearing potential must have a negative serum pregnancy test within 14 days of enrollment. Acceptable contraception should be used while on study and for at least 30 days after the last dose of RAD001.

^c Hematology must include: hemoglobin, hematocrit, platelets, total white blood cell count (WBC) and differential

^d Serum chemistry should be performed while fasting and include: fasting glucose, sodium, potassium, chloride, bicarbonate, creatinine, blood urea nitrogen, albumin, total protein, SGOT (AST), SGPT (ALT), total bilirubin, alkaline phosphatase, calcium, magnesium, phosphate.

^e Fasting serum lipid profile (repeated every three months) must include: total cholesterol, triglycerides, LDL, and HDL

^f Screening radiologic tests include abdominal and pelvic CT or MRI and must be done within 28 days of first RAD001 and temozolomide dose. Radiological scans documenting target lesions should be repeated every two months. If an initial observation of a partial or complete response is made, a confirmation scan should be done no sooner than 4 weeks and no more than 6 weeks after the initial observation. The same type of scan should be used at each evaluation.

^g Assessment of secretory proteins will be performed within 28 days prior to initiation of therapy.

6 Efficacy assessments

The primary efficacy endpoint is objective response rate as determined by radiology review. Important secondary endpoints are response duration and progression-free survival.

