Complete Response: Disappearance of all non-target lesions.

Non-complete response/Non-progression: Persistence of one or more non-target lesions.

Progression: Appearance of one or more new lesions. Unequivocal progression of existing non-target lesions.

Cytology and Histology: if the measurable disease is restricted to a solitary lesion, its neoplastic nature should ideally be confirmed by cytology or histology. These techniques can be used to differentiate between PR and CR in rare cases.

The cytological confirmation of the neoplastic origin of any effusion that appears or worsens during treatment when the measurable tumor has met criteria for response or stable disease is mandatory to differentiate between response, stable disease, and progressive disease

Evaluation of Best Overall Response: the best overall response recorded from the start of the treatment until disease progression/recurrence (taking as reference for progressive disease the smallest measurements recorded since the treatment started). In general, the patient's best response assignment will depend on the achievement of both measurement and confirmation criteria.

Target Lesions	Non-target Lesions	New Lesions	Overall Response
CR	CR	No	CR
CR	Non-CR/Non-PD	No	PR
PR	Non-PD	No	PR
SD	Non-PD	No	SD
PD	Any	Yes or No	PD
Any	PD	Yes or No	PD
Any	Any	Yes	PD

Note:

Patients with a global deterioration of health status requiring discontinuation of treatment without objective evidence of disease progression at that time should be reported as “symptomatic deterioration”. Every effort should be made to document the objective progression even after discontinuation of treatment.

In some circumstances it may be difficult to distinguish residual disease from normal tissue. When the evaluation of complete response depends upon this determination, it is recommended that the residual lesion be investigated (fine needle aspirate/biopsy) before confirming the complete response status.

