6.3 Confirmation Measurement/Duration of Response

Confirmation: To be assigned a status of PR or CR, changes in tumor measurements must be confirmed by repeat studies that should be performed no less than 4 weeks after the criteria for response are first met. In the case of SD, follow-up measurements must have met the SD criteria at least once after study entry at a minimum interval of 6 weeks.

Duration of Overall Response: The duration of overall response is measured from the time measurement criteria are met for CR/PR (whichever is first recorded) until the first date that recurrent or progressive disease is objectively documented (taking as reference for progressive disease the smallest measurements recorded since the treatment started).

The duration of overall complete response is measured from the time measurement criteria are first met for CR until the first date that recurrent disease is objectively documented.

Duration of Stable Disease: Stable disease is measured from the start of the treatment until the criteria for progression are met, taking as reference the smallest measurements recorded since the treatment started.

Progression Free Survival (PFS): PFS is defined as the time from the date of first study treatment to the date of the first documented disease progression or death due to any cause. If a patient has not progressed or died at the date of the analysis cut-off or when he/she receives any further anti-cancer therapy, PFS is censored at the time of the last tumor assessment before the cut-off or the anti-cancer therapy date.

7 Safety assessments

Safety assessments will consist of monitoring and recording all adverse events and serious adverse events, the regular monitoring of hematology, blood chemistry and urine values, regular measurement of vital signs and the performance of physical examinations.

These assessments should be performed within ± 2 days of the scheduled day of assessment except for adverse events that will be evaluated continuously through the study. Safety and tolerability will be assessed according to the NIH/NCI CTCAE <http://ctep.cancer.gov/forms/CTCAEv3.pdf>.

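### Section 10.2 plans Kaplan-Meier for time to response with no censoring rule or analysis set; under the usual censoring the curve would lie above the observed response proportion

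*Combined protocol and SAP*

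**What the plan says.** Section 10.2 (Statistical analysis) gives two methods. The primary analysis is a proportion with its interval: "we will estimate the response rate and provide the associated 95% confidence interval". The method named on the secondary side is different, and the text there reads: "we will use the Kaplan-Meier method to estimate the distributions of time to response and progression-free survival". No cumulative-incidence or competing-risk method is named.

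Section 6.1 sets the window in which a response can count. Best overall response is "the best overall response recorded from the start of the treatment until disease progression/recurrence", and a partial or complete response must be confirmed at least four weeks later.

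The only censoring rule is in Section 6.3 and is written for PFS: "PFS is censored at the time of the last tumor assessment before the cut-off or the anti-cancer therapy date". Time to response has no definition, analysis set or censoring rule.

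Time to response is also not listed as an objective or endpoint. The response-related secondary objective in Section 2 is "To determine the duration of response to the combination of RAD001 and temozolomide in patients with advanced pancreatic neuroendocrine tumors", and Section 6 states: "Important secondary endpoints are response duration and progression-free survival". Section 6.3 defines duration of response, but Section 10.2 gives no method for it.

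**The concern.** Kaplan-Meier treats a censored patient as someone who would go on to have the event at the same rate as those still under observation. A patient who has progressed or died before responding cannot have the event under Section 6.1. Patients may also leave early for other reasons: under Section 4.3, after a dose delay of more than 21 days, "then the patient must be discontinued from the study".

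If these patients are censored at exit, each later response is divided by a risk set that has shrunk for reasons other than response, and the curve rises too steeply. The report would then show a response rate and, from the same patients, a response curve with a higher plateau. The difference always runs in the regimen's favour.

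**Working it through.** The plan states no figure for time to response, so there is none to reproduce. The check compares one minus Kaplan-Meier (1-KM) with the observed proportion responding.

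**Inputs from the documents**
- 32 patients at full dose and a target response rate of 20% (Section 10.1).
- An expected response rate of about 30% for temozolomide-based therapy (Section 1.2).
- Scan interval (Table 5.1 footnote): "Radiological scans documenting target lesions should be repeated every two months".

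**Step 1. Worked example (times assumed).** There are 6 responders among 32, at months 2, 4, 4, 6, 8 and 12, so the observed proportion is 6/32 = 18.75%. Suppose 20 of the 26 non-responders leave, four at each of months 2, 4, 6, 8 and 10, and are censored then. The other six are followed to month 24. The numbers at risk at months 2, 4, 6, 8 and 12 are 32, 27, 21, 16 and 7.

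1-KM = 1 - (31/32)(25/27)(20/21)(15/16)(6/7) = 1 - 0.6865 = 31.4%.

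If only 10 leave, two at each of those months, the numbers at risk are 32, 29, 25, 22 and 17.

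1-KM = 1 - (31/32)(27/29)(24/25)(21/22)(16/17) = 1 - 0.7779 = 22.2%.

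Other handling of the same data:
- Exits treated as competing events (Aalen-Johansen): 18.75% in both cases.
- Non-responders kept in the risk set to the end of follow-up: 18.75%.
- Responders only: the curve reaches 100% and does not estimate a response rate.

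The excess therefore comes from the censoring choice, which the plan leaves open.

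**Step 2. Average size over simulated trials of 32.** Scans are every 8 weeks and the horizon is 48 weeks. Non-responders exit exponentially, with times rounded up to the next scan. Three exit rates were used:
- 65% remaining at week 24: progression-free proportion at 24 weeks in the RAD001-octreotide study, among patients with progression before entry (Section 1.3.2.2).
- 59% remaining: from the 7.3-month median time on temozolomide-thalidomide (Section 1.2). 7.3 months is about 31.7 weeks, and 0.5^(24/31.7) = 0.59.
- 76% remaining: a slower exit rate with no source in the documents.

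Response timing is assumed in three forms: early (60/30/10% at weeks 8/16/24), front-loaded (35/30/20/10/5% at weeks 8 to 40) and even (20% at each of those five scans).

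Mean excess of 1-KM over the observed proportion, in percentage points:

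| True rate | Remaining at week 24 | Early | Front-loaded | Even |
|---|---|---|---|---|
| 20% | 76% | 0.9 | 2.2 | 3.6 |
| 20% | 65% | 1.4 | 3.6 | 6.0 |
| 20% | 59% | 1.8 | 4.6 | 7.5 |
| 30% | 76% | 1.3 | 3.0 | 4.8 |
| 30% | 65% | 2.0 | 4.9 | 7.8 |
| 30% | 59% | 2.5 | 6.2 | 9.9 |

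For scale, the standard error of a proportion from 32 patients is sqrt(0.2 x 0.8/32) = 0.071 at 20% and sqrt(0.3 x 0.7/32) = 0.081 at 30%. The largest entry is 9.9/8.1 = 1.2 standard errors; every early or front-loaded entry is below one.

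**Step 3. A different model.** Let the response probability per two-monthly visit be a constant h, and the exit probability hc = 1 - 0.5^(2/median exit time in months). The true cumulative proportion after K visits is the sum over k = 0 to K-1 of h[(1-h)(1-hc)]^k, while 1-KM tends to 1 - (1-h)^K. With a true 20%, a 12-month median exit and a 12-month horizon, 1-KM is 25.8%, an excess of 5.8 points. Over exit medians of 24 down to 6 months and horizons of 6 to 24 months, it runs from 21% to 47%. The upper end requires responses to keep arriving at an undiminished rate for two years with fast exits, so it is an outer bound and not an expectation.

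**The case against.** The strongest reply is that the plan never says non-responders are censored at exit. That is correct. A reader might infer that Section 10.2 prescribes this censoring, but it prescribes none, and Step 1 shows that two other treatments either remove the excess or change what is estimated. What stands is that Kaplan-Meier is the only method named, and that an analyst given no rule would ordinarily censor patients without the event at their last assessment, as Section 6.3 does for PFS.

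A second reply is that time to response may be a slip for duration of response, where Kaplan-Meier among responders is normal practice. This is plausible, because Sections 2 and 6 list duration and not time to response. It does not remove the point: the sentence needs correcting either way, and the correction must begin by naming the endpoint.

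A reader might also infer that the curve contradicts the primary result or could alter the trial's conclusion. The documents do not support that. The primary analysis is a proportion with a 95% confidence interval, and Section 10.1 decides on a count of three or more responses in 32. Neither uses the curve.

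Nor does it follow that exits must outnumber responses because 70 to 80% of patients are expected not to respond. Many non-responders may simply remain stable: Section 1.2 reports stable disease in 71% of the pancreatic patients on temozolomide-bevacizumab, and Section 1.3.2.2 reports it in 22 of 30 on RAD001-octreotide. Exits after the last response cause no excess.

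Finally, the exit rates fit this trial imperfectly. The 65% comes from 17 patients on another regimen, selected for progression before entry. The 7.3 months is time on treatment in mixed tumour types, where some patients stopped for toxicity, which does not by itself rule out a later response under Section 6.1. This objection to the size stands; the direction does not depend on it.

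**Conclusion.** The point holds as a gap in specification with a predictable direction. If non-responders are censored when they progress, die or leave, 1-KM cannot fall below the observed response proportion, and it exceeds it whenever a response follows such an exit. At a true rate of 20 to 30%, the average excess is roughly 1 to 10 points over 48 weeks. It is near the bottom of that range if responses come early and near the top if they are spread evenly and exits are fast. Response timing is wholly assumed, and the exit rates are borrowed from other regimens or assumed. The primary response rate, its interval and the go/no-go rule are not affected. The change is worth making because the possible error favours the regimen and is easy to prevent, but it concerns a secondary analysis of an endpoint that the plan does not otherwise list.

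**What to change.** In Section 10.2:

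1. State whether time to response or duration of response is meant.
2. If time to response is kept, replace Kaplan-Meier with the cumulative incidence of confirmed response (Aalen-Johansen) in all treated patients. Competing events before response should be progression, death, further anti-cancer therapy, and leaving tumour assessment without a response. The last is needed because patients who stop without starting new therapy would otherwise still be censored, and the curve could still sit above the response rate. Only patients still being assessed at the data cut-off are then censored. Alternatively, report the median and range of time to response among confirmed responders only.
3. Keep Kaplan-Meier for PFS and name it, among responders, for duration of response as defined in Section 6.3.

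The cost is two or three sentences and a standard software option. The scan, progression, death, off-study and subsequent-therapy dates are already needed for PFS and for the off-study record, so no new data are required.

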11.1 General Guidelines for DF/HCC and DF/PCC Institutions

Institutions will register eligible participants with the DF/HCC Quality Assurance Office for Clinical Trials (QACT) central registration system. Registration must occur prior to the initiation of therapy. Any participant not registered to the protocol before treatment begins will be considered ineligible and registration will be denied.

A member of the study team will confirm eligibility criteria and complete the protocol-specific eligibility checklist.

Following registration, participants may begin protocol treatment. Issues that would cause treatment delays should be discussed with the Principal Investigator. If a participant does not receive protocol therapy following registration, the participant's protocol status must be changed. Notify the QACT Registrar of participant status changes as soon as possible.

11.2 Registration Process for DF/HCC and DF/PCC Institutions

The QACT registration staff is accessible on Monday through Friday, from 8:00 AM to 5:00 PM Eastern Standard Time. In emergency situation when a participant must begin treatment during off-hours or holidays, call the QACT registration line at [contact] and follow the instructions for registering participants after hours. Registrations received after 5pm EST aren't processed until the next business morning.

The registration procedures are as follows:

1. Obtain written informed consent from the participant prior to the performance of any study related procedures or assessments.

2. Complete the protocol-specific eligibility checklist using the eligibility assessment documented in the participant's medical/research record. **To be eligible for registration to the study, the participant must meet each inclusion and exclusion criteria listed on the eligibility checklist.**

Reminder: Confirm eligibility for ancillary studies at the same time as eligibility for the treatment study. Registration to both treatment and ancillary studies will not be completed if eligibility requirements are not met for all studies.

3. Fax the eligibility checklist(s) and all pages of the consent form(s) to the QACT at [contact].

Exception: DF/PCC Affiliate sites must fax the entire signed consent form including HIPAA Privacy Authorization and the eligibility checklist to the Network Affiliate Office. The Network Affiliate Office will register the participant with the QACT.

4. The QACT Registrar will (a) validate eligibility, (b) register the participant on the study, and (c) randomize the participant when applicable.
5. The QACT Registrar will send an email confirmation of the registration and/or randomization to the person initiating the registration immediately following the registration and/or randomization. Treatment can not be initiated until after receipt of registration confirmation.

11.3 Registration Process for Other Participating Institutions

Please see section 5.7 in DSMP, Appendix B

12 Data and Safety Monitoring

12.1 Data Reporting

12.1.1 Method

The QACT will collect, manage, and monitor data for this study.

12.1.2 Data Submission

The schedule for completion and submission of case report forms (paper or electronic) to the QACT is as follows:

Form	Submission Timeline
Eligibility Checklist	Complete prior to registration with QACT
On Study Form	Within 14 days of registration
Baseline Assessment Form	Within 14 days of registration
Treatment Form	Within 10 days of the last day of the cycle
Adverse Event Report Form	Within 10 days of the last day of the cycle
Response Assessment Form	Within 10 days of the completion of the cycle required for response evaluation
Off Treatment/Off Study Form	Within 14 days of completing treatment or being taken off study for any reason
Follow up/Survival Form	Within 14 days of the protocol defined follow up visit date or call

12.2 Safety Meetings

The DF/HCC Data and Safety Monitoring Committee (DSMC) will review and monitor toxicity and accrual data from this trial. The committee is composed of clinical specialists with experience in oncology and who have no direct relationship with the study. Information that raises any questions about participant safety will be addressed with the Principal Investigator and study team.

The DSMC will meet quarterly and/or more often if required to review toxicity and accrual data. Information to be provided to the committee may include: up-to-date participant accrual; current dose level information; DLT information; all grade 2 or higher unexpected adverse events that have been reported; summary of all deaths occurring within 30 days for Phase I or II protocols; for gene transfer protocols, summary of all deaths while being treated and during active follow-up; any response information; audit results, and a summary provided by the study team. Other information (e.g. scans, laboratory values) will be provided upon request.

